Subject Payment. All participants will be compensated for their participation. Participants will be paid \$30 for the initial screening/baseline assessment. They will be compensated \$30 for each medication visit (x7), and \$45 for follow up visits. There will be no payment for therapy sessions. Individuals can receive up to a total of \$330 if attending all scheduled treatment and visits. Payment will be made through electronic funds transfer (EFT). Participants will need to provide us with your banking information by completing a special payment form. Alternatively, if participants do not have a bank account, a check will be mailed to them instead. This check(s) will be mailed to the address they provide us with. Patients may choose to receive gift certificates issued to them for use at the VCS canteen (retail store) or VCS cafeteria here at the VACHS in lieu of EFT/check payment. If a patient chooses to receive payment by gift certificate they will be paid for the telemedicine/telehealth visits they participated in at their next in-person visit (e.g. if they complete weeks 2 and 3 by telephone they will receive gift certificates for weeks 2, 3, and 4 at the week 4 visit). Study payments are subject to withholding for outstanding federal debts (i.e., defaulted student loans, interstate child support, back taxes etc) without notification.

Power analysis: The sample size calculation for our primary hypothesis (change in PTSD symptoms) was based on findings from one of the largest and most comprehensive meta-analysis reports on PTSD treatment to date.[36] The report evaluated N=112 studies and reported on 137 comparisons, using validated PTSD symptom measures. The meta-analysis reported that the *effect sizes* for psychotherapy when contrasted with a control group were consistently large and averaged $g=1.14$. Three studies administered CPT specifically and the overall effect size for those was large and averaged $g=1.69$. For this study we conservatively are basing our calculations on a moderate effect size by Cohen's definition.[95] For the First and Second Primary aim we estimate that with 60 subjects randomized to each group we have 80% power to detect a medium effect size ($f=0.25$) at two-sided alpha level of 0.05, and assuming 25% dropout we will recruit a total of N=160.]

Data Analysis:

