Study data will be collected and managed using REDCap electronic data capture tools hosted at VA CT Healthcare System. REDCap (Research Electronic Data Capture) is a secure, web-based application designed to support data capture for research studies, providing 1) an intuitive interface for validated data entry; 2) audit trails for tracking data manipulation and export procedures; 3) automated export procedures for seamless data downloads to common statistical packages; and 4) procedures for importing data from external sources.

Descriptive statistics and graphs will be used to summarize the data on all randomized subjects. All continuous variables will be examined for adherence to the normal distribution using normal probability plots and Shapiro-Wilk tests. Transformations will be applied if needed. If normality is not satisfied and transformations do not help with achieving normality alternative analytic strategies will be considered such as generalized estimating equations (GEE) or nonparametric methods for repeated measures analysis. Baseline demographic and clinical characteristics for the two randomized groups (e.g., age, gender, severity of PTSD, and opiate use) will be compared using chi-square tests for categorical variables and t-tests or nonparametric tests for continuous variables. If there are baseline differences between study treatment groups, these variables will be used as covariates in the mixed-effects models analyses described below. Drop outs and completers will also be compared on baseline characteristics using the same approach. Between group differences in treatment retention, medication compliance and frequency of the occurrence of side effect symptoms across the treatment period will also be assessed. Residual plots and other diagnostics will be used to assess model assumptions.

The primary analyses will be intent-to-treat but sensitivity analyses on completers and non-completers will also be performed. All statistical testing will be at a two-tailed alpha level of 0.05. *Adjustments for multiple comparisons will be conducted among measures in specific domains. In the case of PTSD symptoms (use of 2 measures, PCL-5 and CAPS-5) and opiate use (use of TLFB and urine toxicology) the level of significance will be adjusted to 0.025.*

Primary and Secondary Hypotheses:

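### Testing PCL-5 and CAPS-5 each at a fixed 0.025 is valid but less efficient than Holm, which keeps the same 0.05 family-wise limit and never loses a rejection

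*Combined protocol and SAP*

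**What the plan says.** Section 6 (Research Plan), under Data Analysis, first sets a general level: "All statistical testing will be at a two-tailed alpha level of 0.05". It then states that "Adjustments for multiple comparisons will be conducted among measures in specific domains". Two domains are named. One is PTSD symptoms ("use of 2 measures, PCL-5 and CAPS-5"); the other is opiate use, with TLFB and urine toxicology. For these, "the level of significance will be adjusted to 0.025". No Holm, Hochberg, hierarchical or other stepwise rule appears anywhere.

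Under Primary and Secondary Hypotheses, PCL-5 and CAPS are both primary outcome variables, and the test is the treatment-by-time interaction in a mixed model. Primary Aim 1 has PTSD symptoms measured by PCL-5 and confirmed by CAPS-5. The Power analysis states that "with 60 subjects randomized to each group we have 80% power to detect a medium effect size"; the effect is f = 0.25 and the level is 0.05, not 0.025.

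**The concern.** Halving the level for both measures is the simplest correction for two tests, but not the most powerful one with the same family-wise guarantee. Once one measure has passed at 0.025, only one hypothesis is left to protect, and testing it at 0.05 keeps the family-wise error within 0.05. The fixed rule still holds it to 0.025.

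Take p = 0.01 on one PTSD measure and p = 0.04 on the other. The plan's rule declares the second measure not significant. Holm accepts both, with adjusted p-values of 0.02 and 0.04. Primary Aim 1 looks for agreement between the two measures, so the loss falls on the result the trial most wants to show.

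**Working it through.** **Inputs from the Power analysis.** 60 per group, f = 0.25, two-sided 0.05, stated power 80%. For two equal groups d = 2f = 0.5.

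**Input from Data Analysis.** 0.025 for each of two measures.

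**Assumptions.** The same d = 0.5 on both measures. A two-group comparison stands in for the treatment-by-time test. The correlation between the two test statistics is not in the documents and is varied from 0 to 0.9.

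**Step 1: the plan's own figure.** The mean of z is d√(n/2) = 0.5 × √30 = 2.739. Power at 0.05 is Φ(2.739 − 1.960) = Φ(0.779) = 78.2% (77.5% by noncentral t), close to the stated 80%. Recruitment of 120/(1 − 0.25) = 160 is exact.

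**Step 2: power at the level the plan will use.** Φ(2.739 − 2.241) = Φ(0.497) = 69.0% per measure (68.0% by noncentral t).

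**Step 3: Holm.** A measure is rejected if its |z| exceeds 2.241, or if its |z| lies between 1.960 and 2.241 and the other's exceeds 2.241. Both are rejected if both |z| exceed 1.960 and at least one exceeds 2.241.

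At correlation 0 this can be done by hand. The chance of falling between the two limits is 0.7819 − 0.6905 = 0.0914.
- Per measure: 0.6905 + 0.0914 × 0.6905 = 0.754.
- Both, fixed rule: 0.6905² = 0.477.
- Both, Holm: 0.7819² − 0.0914² = 0.603.

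The same events under a bivariate normal distribution give:

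| Correlation | Per measure: fixed → Holm | Both: fixed → Holm | At least one, either rule |
|---|---|---|---|
| 0 | 69.0% → 75.4% | 47.7% → 60.3% | 90.4% |
| 0.5 | 69.0% → 74.4% | 54.5% → 65.2% | 83.6% |
| 0.7 | 69.0% → 73.9% | 57.9% → 67.6% | 80.2% |
| 0.9 | 69.0% → 73.0% | 62.7% → 70.7% | 75.4% |

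The gain is about 4 to 6 points per measure and 8 to 13 points for both.

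**Step 4: other conditions.**
- All 80 per arm contributing, correlation 0.7: 82% → 86% per measure and 74% → 82% for both.
- d = 0.5 on one measure and 0.3 on the other: power for both gains 9 to 10 points. Most of this is on the weaker measure (7 to 10 points, against 0 to 2.5 on the stronger).
- No effect on one measure: the other gains at most 0.2 points.

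**Step 5: error rates.** With no effect on either measure, the family-wise error is identical under the two rules: 0.049 at correlation 0 and 0.036 at 0.9. With no effect on one measure and d = 0.5 on the other, correlation 0.7, the null measure is falsely rejected 2.5% of the time under the fixed rule and 3.9% under Holm. With a stronger true effect on the other measure (mean z = 4) the figures are 2.5% and 4.6%. The limit is 5%.

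**The case against.** The strongest reply is that nothing is broken. The 0.025 split is prespecified and controls the error it claims to control. That stands: this is a gain in efficiency and not the correction of an error.

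A second reply is that the decision rule should be settled first, since the plan does not say whether Primary Aim 1 needs one measure or both.
- If either suffices, Holm adds nothing, because power for at least one is the same.
- If both are required, each can be tested at 0.05 with no split. At correlation 0.7 that gives 69.0% for both, against Holm's 67.6%.
- If CAPS-5 only confirms PCL-5, a fixed sequence gives PCL-5 78%, against Holm's 74%.

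These are fair alternatives, but each needs a decision rule that the plan does not state. None shows the fixed split to be better than Holm when each measure is to be judged separately.

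A third reply concerns cost, and it also stands. A reader might infer that Holm gives up nothing in error control. In fact the fixed rule caps each measure's own false-positive rate at 0.025, and Holm lets it approach 0.05 when the other measure has a true effect. Intervals need care too. Every added rejection has a p-value between 0.025 and 0.05, so a 97.5% interval would include no effect in each of those cases.

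Finally, equal effect and precision on the two measures is not supported by the documents. Table 1 schedules CAPS far less often than PCL-5.

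**Conclusion.** The point holds as an inexpensive improvement to a valid rule. That Holm keeps family-wise error at or below 0.05 and never loses a rejection does not depend on any assumption here. The size of the gain does: 69% to 73-75% per measure, and 48-63% to 60-71% for both, rest on d = 0.5 on both measures, 60 per arm, a two-group approximation and an assumed correlation of 0 to 0.9.

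Three stronger readings are tempting but not supported.
- **Holm repairs the power statement.** It does not. Going from 0.05 to 0.025 costs 78.2 − 69.0 = 9.2 points per measure. Holm recovers roughly half, so the 80% calculated at 0.05 still does not describe a test that starts at 0.025.
- **The gain covers opioid use in the same way.** The hypotheses section describes TLFB as confirmed with urine toxicology and names frequency of opioid use as the dependent measure. Whether the two are tested separately is unclear, and the gain applies only if they are.
- **Pain is held to the same split.** The 0.025 sentence names only PTSD symptoms and opiate use. The NRS and PROMIS-29 hypotheses are exploratory, so they are outside this point.

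**What to change.** In Data Analysis, replace the fixed 0.025 for PTSD symptoms with: *The two p-values are tested by the Holm procedure at a family-wise 0.05: the smaller at 0.025 and, if significant, the larger at 0.05.* Apply the same sentence to opioid use only if the plan also states that TLFB and urine toxicology are tested separately.

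Report Holm-adjusted p-values. Beside them give either 95% intervals labelled as unadjusted or Holm-compatible intervals, and state that significance is judged by the adjusted p-values. Do not use 97.5% intervals, which would contradict the added rejections.

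The plan should also state the trade-off: a single null measure can be falsely rejected at a rate above 0.025, though not above 0.05, when the other measure has a true effect.

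The change costs a few lines of text, made before outcome data are compared by arm. It needs no additional participants, visits or data. The lasting cost is less simple matching intervals.

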Primary Aim 1: To test whether CPT is more effective than IDC in treating symptoms of PTSD among Veterans and civilians with OUD maintained on buprenorphine. PTSD symptoms will be measured using the PTSD Checklist – Military version (PCL-5), and confirmed by the Clinician Administered PTSD Scale using the DSM-5 criteria (CAPS-5).

Secondary Aim 1: To test whether CPT- is more effective than IDC in reducing opioid use among Veterans and civilians with PTSD and comorbid OUD maintained on buprenorphine. Opioid use will be measured using the Timeline Follow-back (TLFB) and confirmed by urine toxicology results.

Exploratory Aims: To examine if treatment groups differ in 1) *retention*, measured by days in treatment, 2) *psychosocial functioning*, measured by the *participants RAND 12-Item Short Form Health Survey (VR-12)*, 3) *sleep* as measured by the *Insomnia Severity Index (ISI)*, since sleep disturbance is a hallmark of PTSD and during early abstinence from opioids, and 4) Because of the high comorbidity between PTSD and chronic pain we will explore this relationship and will measure *pain intensity* (measured by the Numeric Rating Scale (NRS), and *functional impairment* using the PROMIS-29 (Patient-Reported Outcomes Measurement Information System) longitudinally over the course of treatment. Follow up will be conducted 1 and 3 months after completion of the study to evaluate *durability of effect on PTSD symptoms (measured as changes in PTSD symptoms), opioid use and treatment utilization*.

4-5. BACKGROUND AND SIGNIFICANCE:

This proposal was originally developed in collaboration with the Consortium to Alleviate PTSD (CAP) ([name] Director and [name] co-Director), underwent scientific review and was proposed for funding. However, CAP was unable to fund it as buprenorphine treatment is of limited importance for active-duty personnel. The CAP leadership group encouraged our group to send this application to the VA as it has great clinical relevance for the VA and for Veterans, *although CAP is no longer involved in this proposal*. Please see the attached letter of support.

A. Posttraumatic stress disorder (PTSD)

i) PTSD is a serious psychiatric disorder that can occur after the experience of a traumatic event.

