For the primary and secondary hypotheses, we will use mixed effects models to assess changes in PTSD symptoms and opiate use over time. Treatments will be used as between-subject factors and time (in weeks) will be used as a within-subject factor. The primary outcome variables will be PTSD symptoms as measured by generated from the PCL-5 and CAPS scales. The secondary outcome variables will be frequency of opiate use generated from the TLFB and confirmed with urine toxicology results each medication visit (weeks 1-4, 6, 8, 12) and follow-up. The use of the mixed-effects models approach for the analysis of our longitudinal data has several specific advantages. Unlike traditional repeated measures analyses, mixed effects models allow for different numbers of observations per subject, use all available data on each subject and are unaffected by randomly missing data. They also provide flexibility in modeling the correlation structure of the data.[96]

Primary Aim 1. We hypothesize that CPT will significantly reduce PTSD symptoms compared to IDC in Veterans and civilians with PTSD and comorbid OUD maintained on buprenorphine.

This hypothesis will be tested by the interaction of treatment (CPT vs. IDC), and time in the mixed model specified above. Significantly greater decrease in PTSD symptoms in the CPT group will be considered supportive of the hypothesis.

Secondary Aim 1. We hypothesize that CPT will significantly reduce opioid use compared to IDC in Veterans and civilians with PTSD and comorbid OUD maintained on buprenorphine.

This hypothesis will be tested by the same approach as described in primary aim 1 but with frequency of opioid use as the dependent measure.

Exploratory Hypothesis:

We hypothesize that CPT will significantly improve retention (days in treatment) compared to IDC in Veterans and civilians with PTSD and comorbid OUD maintained on buprenorphine.

This hypothesis will be tested using ANOVA or nonparametric equivalent comparing the two treatment groups (CPT vs. IDC).

We hypothesize that CPT will significantly improve psychosocial functioning (measured by the VR-12 survey) compared to standard counseling in Veterans and civilians with PTSD and comorbid OUD maintained on buprenorphine.

This hypothesis will be tested by the interaction of treatment (CPT vs. IDC) and time.

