We hypothesize that CPT will significantly improve sleep (measured by the ISI) compared to standard counseling in Veterans and civilians with PTSD and comorbid OUD maintained on buprenorphine.

This hypothesis will be tested by the interaction of treatment (CPT vs. IDC) and time.

We hypothesize that CPT will significantly reduce pain intensity (measured by the NRS) and improve functional impairment due to pain (measured by the PROMIS-29) when compared to standard counseling during 12 weeks of treatment in Veterans and civilians with PTSD and comorbid OUD maintained on buprenorphine.

These hypotheses will be tested by the interaction of treatment (CPT vs. IDC), and time (four time points during treatment) in the mixed model. ***We propose to follow up Veterans and civilians 1 and 3 months after completion of the study to evaluate changes in PTSD symptoms, opioid use and treatment utilization.*** This analysis is exploratory and will assess change over time in symptoms and treatment using mixed-effects models with two factors (study treatments [CPT vs. IDC], and time (end of treatment, 1 month, and 3 months follow up)).

Potential Risks and Adequacy of Protection from Risks

Potential Risks: There are potential risks, discomforts and inconveniences associated with participation in this study. These may be due to buprenorphine maintenance, Cognitive Processing Therapy (CPT), standard (drug) counseling, and nonspecific risks such as loss of confidentiality.

a) All subjects will be treated with buprenorphine maintenance. Buprenorphine is a partial μ -opioid agonist and a weak κ -opioid antagonist available alone or in combination tablet containing buprenorphine and naloxone in a ratio of 4:1. In this study, a combination tablet will be used, since it is less likely to be diverted than the buprenorphine only formulation. The doses of buprenorphine/naloxone used here are within the recommended guidelines of the manufacturer. Consistent with the clinical guidelines, before BUP/NLX is administered, participants will be instructed not to use any prescription opioids for 24 hours and be prepared to stay in the clinic for at least 2 hours following the first dose of BUP/NLX. [During induction into buprenorphine, all participants will be started at a dose of 2mg, and this dose will be increased up to 32 mg per

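### The exploratory durability model leaves out baseline and on-treatment scores, so the 3-month CPT–IDC difference can be biased, in either direction, if dropout differs by arm

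*Combined protocol and SAP*

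**What the plan says.** Under Exploratory Hypothesis in the Data Analysis part of the Research Plan, the follow-up analysis is described thus: "This analysis is exploratory and will assess change over time in symptoms and treatment using mixed-effects models with two factors". The factors are study treatment and "time (end of treatment, 1 month, and 3 months follow up". Under Specific Aims, the purpose of follow-up is to evaluate "durability of effect on PTSD symptoms (measured as changes in PTSD symptoms), opioid use and treatment utilization".

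Earlier scores exist. Table 1 schedules the PCL-5 and the TLFB at baseline, at on-treatment visits and at follow-up. For opioid use, Primary and Secondary Hypotheses lists "each medication visit (weeks 1-4, 6, 8, 12) and follow-up". That section also justifies mixed models because they "use all available data on each subject and are unaffected by randomly missing data".

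Three further points bear on this:
- Baseline can enter conditionally: "If there are baseline differences between study treatment groups, these variables will be used as covariates in the mixed-effects models analyses described below".
- On the analysis population: "The primary analyses will be intent-to-treat but sensitivity analyses on completers and non-completers will also be performed".
- The plan does not say whether people who stop study treatment are still assessed at week 12, month 1 and month 3.

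**The concern.** A likelihood-based mixed model is protected against missing data only so far as the scores that predict missingness are in the model. The primary model has them. The durability model starts at end of treatment and does not. Someone who left at week 6 with a high PCL-5 and was not seen again has informative scores on file, none of which enters.

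The protocol gives reasons to expect loss that is related to symptoms and differs by arm:
- The Exploratory Hypothesis section expects better retention with CPT.
- Potential Risks (b) says CPT may raise PTSD symptoms early in therapy.
- Potential Risks (c) says PTSD is not addressed under IDC and may worsen.
- Protection Against Risk provides for withdrawal of participants who deteriorate severely.

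There is also a question of contrast. A treatment-by-time interaction that begins at end of treatment is zero if a benefit persists in full, and equally zero if there never was one. It does not by itself say whether an effect is present at 3 months. At stake is the trial's only evidence on durability.

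**Working it through.** **The plan's own figure.** The durability analysis has no sample-size figure of its own. The trial total reproduces: 2 × 60 = 120, and 120 / (1 − 0.25) = 160 (Power analysis). For two groups f = 0.25 is d = 0.5; power with 60 per arm at two-sided 0.05 is 0.78, close to the stated 80%. If leavers are not assessed again, the three-level model holds 160 × 0.75 = 120 participants, or 160 × 0.70 = 112 at the 30% dropout given in the Overview.

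**Large-sample simulation.** Inputs from the documents: visits at baseline, weeks 1–4, 6, 8 and 12, then months 1 and 3 (set at weeks 16 and 24); loss of 25% or 30%; effect 0.5 SD. Assumptions not in the documents:
- The true CPT–IDC difference is −0.50 SD from week 12 on.
- Correlation between scores Δ weeks apart is 0.5 + 0.5 × 0.95^Δ, which is 0.77 at 12 weeks.
- Log-odds of leaving before each visit up to week 12 are c + 0.7 × (last observed score) where loss is score-driven, and c where it is random, with c set to reach the stated loss.
- Leavers are not seen again.

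There are 100,000 participants per arm. Monte Carlo error is about sqrt(2/75,000) = 0.005 SD. Both models are fitted by maximum likelihood.

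| Loss before week 12 | CPT / IDC loss | 3-month difference, three-level model | 3-month difference, all-visit model | Interaction, three-level model (truth 0) |
|---|---|---|---|---|
| Random | 25 / 25% | −0.50 | −0.50 | 0.00 |
| Random, unequal | 40 / 20% | −0.49 | −0.49 | 0.00 |
| Score-driven, same in both arms | 25 / 25% | −0.50 | −0.50 | 0.00 |
| Score-driven in IDC only | 25 / 25% | −0.38 | −0.50 | −0.03 |
| Score-driven in IDC only | 30 / 30% | −0.35 | −0.50 | −0.04 |
| Score-driven in CPT only | 25 / 25% | −0.63 | −0.50 | 0.02 |
| Score-driven in CPT only | 30 / 30% | −0.65 | −0.50 | 0.04 |
| Same score dependence, unequal rate | 20 / 40% | −0.38 | −0.49 | −0.02 |
| Same score dependence, unequal rate | 40 / 20% | −0.61 | −0.50 | 0.02 |
| Opposite dependence (worse leave CPT, better leave IDC) | 25 / 25% | −0.73 | −0.49 | 0.06 |
| Opposite dependence | 30 / 30% | −0.81 | −0.51 | 0.07 |

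Setting aside the extreme last pattern, the bias where the arms differ in score-driven loss runs from 0.61 − 0.50 = 0.11 to 0.50 − 0.35 = 0.15 SD, with either sign. In the last pattern it is 0.23 to 0.31 SD.

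**Lower correlations.** With correlations of 0.66 at 4 weeks and 0.50 at 12 weeks, and about 25–28% with none of the three scores, score-driven loss in IDC only gave 0.36, and the same mechanism in both arms gave 0.48. The all-visit model gave 0.50 in both cases.

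**What the interaction can show.** With 60 per arm seen at both times, the standard error of the difference in change is sqrt(4(1 − r)/60): 0.183 SD at r = 0.50 and 0.124 SD at r = 0.77. Power to detect loss of half of a 0.5 SD effect (0.25 SD) at two-sided 0.05 is Φ(0.25/0.183 − 1.96) = 0.28 and Φ(0.25/0.124 − 1.96) = 0.52. A null result would be weak evidence that a benefit had lasted.

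**The case against.** The strongest reply is that the planned target is change, not the 3-month difference: the aims speak of "durability of effect on PTSD symptoms (measured as changes in PTSD symptoms", and the post-treatment interaction is nearly unbiased in every pattern above. That stands for the interaction. But the aim is durability of effect, and change after week 12 does not settle that without the difference itself.

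A reader might go further than the documents allow in four ways:
- **That the 3-month difference is biased, and diluted.** Bias requires loss that depends on earlier scores and differs by arm in rate or mechanism. Its direction is not known; the early symptom rise described for CPT points away from simple dilution.
- **That early leavers drop out of the analysis.** This is so only for those with none of the three scores. Stopping therapy is not missing follow-up. The follow-up visits are by telephone or telemedicine and are paid, and the plan is silent on whether leavers are assessed.
- **That durability will be declared from a non-significant interaction.** The plan states no decision rule.
- **That IDC loss could exceed half.** In the preliminary chart review 25 of 46 patients with PTSD (54%) were not retained at 3 months. That is non-randomised clinic retention among all such patients, not missed trial assessments in an IDC arm.

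Also fair: baseline is not wholly excluded, since it may become a covariate if the arms differ, though that brings back no one without a later score. The opioid-use text already mentions follow-up alongside the treatment visits and can be read as one all-visit model. The analysis is exploratory, and with 60 per arm the standard error of a 3-month difference is about sqrt(2/60) = 0.18 SD, larger than the 0.11–0.15 SD bias. These points limit the seriousness but do not argue for leaving collected data out.

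**Conclusion.** The point holds as a conditional one. The three-level model omits scores that the trial collects and so weakens the missing-data protection on which the plan relies. At about 25–30% loss, a true 3-month difference of 0.5 SD can be misestimated by roughly 0.1 to 0.15 SD in either direction if score-dependent loss differs by arm. If dropout is the same in both arms the error is about zero. The post-treatment interaction moves by at most about 0.07 SD, and the primary analysis is not affected.

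The sizes rest on assumed correlations, an assumed strength of dropout and no assessment after leaving. The all-visit model removes the bias only where loss depends on observed scores. Separately from dropout, the interaction from end of treatment does not by itself establish that an effect is present at 3 months.

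**What to change.** Replace the separate three-level model, for PTSD symptoms and for opioid use, with one mixed model per outcome. Time should be categorical and include baseline, every on-treatment visit and months 1 and 3. From it report:
- the CPT–IDC difference with its confidence interval at end of treatment, 1 month and 3 months;
- the change in that difference from week 12 to month 3, with its interval.

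Keep the exploratory label. Add a sentence saying whether participants who stop study treatment are still assessed at week 12 and at follow-up, and make the opioid-use text and the follow-up text agree on which model covers follow-up.

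The gain is mainly for the PCL-5 and TLFB. It is small for the CAPS-5, which is planned only before and after treatment and at follow-up. The cost is plan wording only: the data are already scheduled and the model class is the same.
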